#### **11. Safety Monitoring Plan**

Data and safety monitoring for this study will be provided by the Clinical Science Research & Development (CSR&D) centralized Data Monitoring Committee (DMC). The DMC is provided by CSR&D to ensure independent oversight of the safety and integrity of the project. The DMC is an independent multidisciplinary group, whose members have collectively – through research, education, training, experience, and expertise – the requisite knowledge pertinent to the subject areas to be reviewed. Membership details are available on the CSRD website. The DMC will provide an ongoing independent evaluation of this study focused on safety and feasibility, including participant accrual and retention, adverse events monitoring, and data analyses. Meetings will be held three times per year at which recommendations will be made to the Director of CSR&D for endorsement. These recommendations will range from approval to continue (unconditionally or with conditions to be addressed) to probation or possibly termination, if there are problems with enrollment or safety concerns.

The PI will be responsible for providing these quarterly summaries to the local IRB and CSR&D as part of the annual review process. In addition, the PI will be responsible for executing any recommended changes to DMC and complying with the reporting requirements.

#### **Protocol for Monitoring Adverse Events**

Because of the psychiatric nature of the sample to be studied, there is a potential for adverse events to occur. These adverse events include suicidal ideation, homicidal ideation, and an increase in PTSD and depression symptom severity. Although the likelihood of these adverse events occurring in response to PTSD treatment is low (e.g., Foa et al., 2002; Sloan et al., 2018), these adverse events will be closely monitored throughout the study. Apart from these potential adverse events, we do not anticipate the occurrence of any other adverse events related to the treatments to be examined.

There are two reasons suicidal risk will be assessed in the proposed study. The first reason is to determine participant eligibility and the second reason is to ensure the safety and well-being of participants throughout the study. We will assess suicidal risk using the Mini International Neuropsychiatric Interview (MINI) suicide module at each assessment occasion. The MINI suicide module is a clinician administered interview that consists of 9 questions related to suicidal ideation and behaviors, with possible scores ranging from 0 to 53. Low suicide risk is defined as 0-8 points, moderate suicide risk is defined as 9-16 points, and high suicide risk is defined as scoring 17 or greater. We have decided to use this measure because the MINI suicide module is clinician-administered, includes clear guidelines for determining suicide risk, and requires approximately 10 minutes to administer. The MINI demonstrates excellent inter-rater reliability, with kappa values exceeding 0.75 (Lecrubier et al., 1997; Sheehan et al., 1998); and generally good test-retest reliability, with kappa values typically exceeding 0.65 (Lecrubier et al., 1997; Sheehan et al., 1998). Individuals will be excluded from enrolling in our proposed randomized controlled trial if they score 17 or higher (high risk) on the MINI suicide module at the initial assessment. Individuals who are excluded from participating in the clinical trial will be provided with appropriate clinical referrals. The PI will follow up with each of these individuals within one week to make sure they have connected with appropriate clinical care.

To monitor suicide risk throughout the treatment phase, we will administer the BDI-II at each treatment session. If a participant endorses suicidal ideation at any level in response to question #9 (suicidal thoughts or wishes), a licensed psychologist will administer the MINI suicidal module. Participants deemed to be a high risk for suicide on the MINI (i.e., score of 17 or higher) will be removed from the study treatment and appropriate actions will be taken. These actions are described below in the data monitoring section. In addition, if the participant is willing, they will continue to be followed by the PI.

Homicidal risk will be assessed using approach recommended by *VA/DOD Clinical Practice Guideline for Major Depressive Disorder* (2009). At the initial assessment and at the beginning of each treatment session, participants will be directly asked whether they have thoughts of harming anyone. If the participant indicates they do have thoughts of harming someone, then the clinician will ask whether the participant has an active plan or method to harm someone (e.g., weapon in their home) and whom the participant wishes to harm. Further assessment will take place for participants who indicate that they have an active plan or method. Specifically, they will be asked whether they have ever lost control and acted violently and, if so, the severity of reported past violent behavior will be assessed. If a participant indicates that they have thoughts of harming someone and they have an active plan, the participant will be considered potentially high risk and further assessment will be conducted, as described in the section on managing adverse events.

We will monitor for a substantial increase in PTSD symptom severity during the treatment phase using the Posttraumatic Check List for DSM-5 (PCL-5). The PCL-5 is a 20 item self-report measure

of PTSD symptom severity. This measure will be completed at each assessment session and each treatment session. A substantial increase in symptoms is defined as at least 10-point increase in PTSD from the initial assessment and has been sustained for a three-week period (e.g., Foa et al., 2002).

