#### *Safety Monitoring Measures*

The **PTSD Checklist for DSM-5 (PCL-5)** (Weathers, Litz, et al., 2013) will be administered at each assessment occasion, including baseline, and the beginning of every treatment session to monitor for symptom worsening, defined as an increase from the initial assessment of at least 10 points that is sustained for at least three consecutive treatment sessions (Foa, Zoellner, Feeny, Hembree, & Alvarez-Conrad, 2002). The PCL-5 is completed in reference to the identified criterion A event established at the baseline assessment. This is a psychometrically strong measure that is sensitive to change (Weathers et al., 2013; Bovin et al., 2016) and requires no more than 5-10 minutes to complete.

The **Beck Depression Inventory-II (BDI-II)** (Beck et al., 1996) is a 21-item self-report measure assessing current depressive symptoms and has well-established reliability and validity (Dosois et al., 1998). The BDI-II will be administered at each assessment occasion, including baseline, and the beginning of every treatment session to monitor exacerbation of depression symptoms associated with treatment, as well as to assess any changes in suicidal ideation. This measure requires no more than 5-10 minutes to complete.

The **Self-Injurious Thoughts and Behaviors Interview (SITBI)** (Nock et al., 2007) is a structured clinical interview that assesses the presence, frequency, and characteristics of a wide range of self-injurious thoughts and behaviors, including suicidal ideation, suicide plans, suicide gestures,

suicide attempts, and nonsuicidal self-injury. The SITBI has demonstrated excellent psychometric properties in multiple samples, including strong interrater reliability, and test-retest reliability over a 6-month period. Moreover, concurrent validity was demonstrated via strong correspondence between the SITBI and other measures of suicidal ideation, suicide attempt, and nonsuicidal self-injury. This interview takes approximately 20 minutes to administer.

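### Homicidal ideation is to be monitored for the whole study, but no question about it is scheduled at the 10-, 20- and 30-week interviews

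*Combined protocol and SAP*

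**What the plan says.** Section 11, Protocol for Monitoring Adverse Events, lists suicidal ideation, homicidal ideation, and worsening of PTSD and of depression symptoms as the adverse events to expect, and states that "these adverse events will be closely monitored throughout the study".

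The same section then sets out how each is watched:

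- **Homicidal ideation:** "At the initial assessment and at the beginning of each treatment session, participants will be directly asked whether they have thoughts of harming anyone". A positive answer leads to questions about plan, method and target.
- **Suicide risk:** "We will assess suicidal risk using the Mini International Neuropsychiatric Interview (MINI) suicide module at each assessment occasion". A score of 17 or more counts as high risk.
- **PTSD worsening:** "We will monitor for a substantial increase in PTSD symptom severity during the treatment phase". Of the PCL-5 it says: "This measure will be completed at each assessment session and each treatment session".
- **Depression:** section 8, Safety Monitoring Measures, schedules the BDI-II at every assessment and every treatment session.

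Assessments take place at baseline and at 10, 20 and 30 weeks after the first treatment session (section 7, Assessment Schedule). The Table of Assessment Schedule in section 8 has no row for the homicidal-ideation question.

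**The concern.** The stated aim covers the whole study, but the rule for asking stops with the last treatment session. Followed exactly, it leaves a named safety event unasked at three interviews that are going to happen anyway.

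The person at issue is a participant who, after treatment, has thoughts of harming someone, is not at high suicide risk, shows no PTSD increase that would prompt a call from the investigator, and does not raise the matter. The duty to report explicit intent against a named individual (section 11, Protocol for Managing Adverse Events) can be met only if the thoughts come to light.

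Because the questions are tied to sessions, ideation is also looked for more often and for longer in PE than in WET. No analysis of this event is planned, so this has no bearing on the trial's conclusions.

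**Working it through.** **Does another follow-up measure fill the gap?** Three instruments given at weeks 10, 20 and 30 address risk.

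- SITBI (section 8): it "assesses the presence, frequency, and characteristics of a wide range of self-injurious thoughts and behaviors".
- MINI suicide module (section 11): "The MINI suicide module is a clinician administered interview that consists of 9 questions related to suicidal ideation and behaviors".
- BDI-II item 9 (section 11): suicidal thoughts or wishes.

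None is described as asking about harm to others. The other three named events each have a scheduled measure at follow-up: a suicide interview, the PCL-5 and the BDI-II. Only suicide risk has an explicit threshold there, since the PTSD-worsening rule is a treatment-phase rule. Homicidal ideation has no scheduled measure at all.

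**Inputs for the size of the gap.** WET has 5 weekly sessions plus up to 2 repeats, so 5 to 7. PE has 8 to 15 weekly sessions (both from Interventions). There are 90 participants per arm (section 6), and follow-up ends at week 30. The plan gives no figure of its own to reproduce.

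**Weekly attendance, full course.** Session n falls at week n − 1, so the gap to week 30 is 30 − (n − 1).

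| Arm | Sessions | Last question | Gap (weeks) | Share of 30 weeks |
|---|---|---|---|---|
| WET | 5 | week 4 | 26 | 87% |
| WET | 7 | week 6 | 24 | 80% |
| PE | 8 | week 7 | 23 | 77% |
| PE | 15 | week 14 | 16 | 53% |

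Follow-up interviews after the last question: all 3 in WET; in PE, 3 for courses of 8 to 10 sessions and 2 for 12 to 15 (session 11 falls in week 10 itself). The total is 90 × 3 + 90 × 2 = 450 up to 90 × 3 + 90 × 3 = 540, out of 180 × 3 = 540.

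**One session every two weeks (assumed).** Section 7 expects completion times to vary. Session n now falls at week 2(n − 1).

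- WET: last question at week 8 to 12; gap 22 down to 18 weeks; 3 or 2 interviews after it.
- PE: last question at week 14 to 28; gap 16 down to 2 weeks; 2 or 1 interviews after it.
- Total: 90 × 2 + 90 × 1 = 270 up to 90 × 3 + 90 × 2 = 450, out of 540.

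**Early dropout.** Someone who stops after session 1 has 30 − 0 = 30 weeks without a question, yet is asked to complete every assessment. At the dropout rates in section 5, early stoppers would number 0.36 × 90 ≈ 32 in PE and 0.05 × 90 = 4.5 to 0.10 × 90 = 9 in WET. The 36% is given for first-line PTSD treatments together, so its use for PE alone is an approximation.

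**With the question added at weeks 10, 20 and 30.** The successive gaps after the last session, with weekly attendance, become:

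- WET: 4 to 6, 10, 10
- PE, 8 sessions: 3, 10, 10
- PE, 12 sessions: 9, 10
- PE, 15 sessions: 6, 10
- Stopped after session 1: 10, 10, 10

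The longest gap is 10 weeks for anyone who attends. Assessment visits at which both arms are asked rise from 1 (baseline) to 4. Counting sessions 1 to 5 as well, common time points rise from 6 to 9.

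**The case against.** The best reply is that the commitment to whole-study monitoring is a general lead-in, and that the detail beneath it concentrates active monitoring on the treatment phase for more than one event. Reducing active questioning once exposure work ends is a defensible choice. The plan also has other routes:

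- The Protocol for Managing Adverse Events says what an assessor does if suicidal or homicidal ideation comes up in a telephone assessment.
- Participants are given numbers to call if they feel homicidal, and are told to make contact about worsening during follow-up (section 10, Protection against risk).
- High suicide risk or a PTSD increase brings the investigator into contact.
- Participants removed from treatment for safety are followed if they agree.

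The plan itself rates these events as unlikely in response to treatment, and an independent committee reviews safety.

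Much of this stands as context. Monitoring does taper for other events, and the remaining gap is a narrow one. But each of these routes responds to a disclosure or to a different trigger, and none schedules a question. The sentence on telephone assessments shows that the plan expects such disclosures, which is a reason to ask.

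Two further points are accepted. The assessment table is weak evidence: it also lacks a row for this question at baseline and treatment sessions, where the text does schedule it, and it has no MINI row. The case therefore rests on the text. And the count of 450 to 540 interviews depends on weekly attendance; the two-weekly count of 270 to 450 belongs beside it.

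**Conclusion.** The concern holds. Homicidal ideation is a named adverse event with a stated commitment to monitoring for the whole study, yet zero questions about it are scheduled at the three follow-up interviews.

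On the nominal weekly calendar the unasked period is 24 to 26 weeks in WET and 16 to 23 in PE. At one session every two weeks it is 18 to 22 and 2 to 16. These are weeks and visits without a question, not missed events: the documents give no rate from which to estimate those.

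The consequence is confined to safety. The change should be made because the risk is one the plan itself names, the response pathway already exists, and the cost is small.

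**What to change.** Extend the sentence in the Protocol for Monitoring Adverse Events so that the direct question is also asked at the 10-, 20- and 30-week assessments, and add a row to the Table of Assessment Schedule showing every time point. At follow-up the evaluator asks the question. If the answer is yes, the evaluator goes on to the existing questions on plan, method and target, and then alerts the PI or site PI under the Protocol for Managing Adverse Events. Add a short briefing on this to the evaluator training in section 7, which at present describes the CAPS-5 and MINI only.

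Cost, with timings assumed:

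- Questions: at most 180 × 3 = 540, at 1 minute each = 9 hours, within interviews already planned.
- Follow-up enquiries: if 1% to 5% of answers are positive (assumed), 540 × 0.01 ≈ 5 to 540 × 0.05 = 27, at 10 minutes each = 0.9 to 4.5 hours.
- Briefing: 1 hour for 3 to 6 evaluators (number not stated, assumed) = 3 to 6 hours. This may be partly needed already, since the question is due at the initial assessment.
- Total: 9 + 0.9 + 3 = 12.9 to 9 + 4.5 + 6 = 19.5 evaluator hours over the trial.

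Up to 5 to 27 investigator calls and the work of processing the amendment come on top of that total.

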### **Protocol for Managing Adverse Events**

In the event a participant is deemed high suicide and/or homicidal risk, staff will immediately locate the PI or site PI, both of whom are licensed psychologists. The PI or site PI will intervene by a) following up with direct questions about suicidal/homicidal behaviors, b) assess mental status by asking about psychotic symptoms, mood symptoms and drug and alcohol use, c) schedule extra contacts if necessary, emphasizing problem solving, d) help the participant generate short-term objectives, and e) negotiate an action plan. The action plan will be collaboratively generated by the investigator and the participant. The plan will address what actions need to be taken in the succeeding days to solve the problems that precipitated suicidal/homicidal behavior. The plan will also address the use of voluntary and involuntary hospitalization, if necessary. Lastly, in the case of homicidal ideation with explicit intent to harm a named individual, the PI will report the intent to the local police as required legally required to protect the named individual. This procedure will be the same for SI/HI that is uncovered during the course of telephone assessments. That is, the assessor will alert the PI or site PI who will then reach out to the veteran via telephone and take appropriate clinical action.

In addition to these formal assessments, all participants will be given the number of the on-call psychiatry service at the respective VA site and informed that they should call this number after business hours in the event that they are feeling suicidal and/or distressed, or homicidal. This is the local IRB policy for clinical trials conducted at the two VA recruitment sites. During business hours the participants will be instructed to contact the contact the PI (VABHS) or site PI (RHJVA). Should a participant call to indicate suicidal/homicidal risk, then the previously described intervention plan will be followed. Participants will also be informed during the informed consent process that if suicidal and/or homicidal intentions are disclosed confidentiality may be broken in order for protective measures to be taken. The suicidal risk management plan has empirical support for its efficacy (Chiles & Strosahl, 2005) and is the plan that is recommended for use by the American Psychiatric Association. Moreover, the homicidal risk assessment and management plan is recommended by *VA/DoD Clinical Practice Guidelines* (2009).

In the event that a participant experiences an increase in PTSD symptom severity but without suicidal/homicidal risk, the PI or site PI will intervene by asking direct questions about the nature and causes of the distress, conduct a PTSD assessment, and schedule extra contacts (assessments) if deemed necessary. Such individuals will be withdrawn from study treatment from the protocol if they report a substantial increase in the PTSD symptom severity (i.e. at least 10 points higher than their baseline PTSD symptom severity score) that is sustained over a three-week period and the cause of the increase is determined to be related to the study treatment. We have selected

the 10-point increase and 3-week time frame based on Foa, Zoellner et al. (2002) in which they emphasize the importance of using a reliable index score when considering increases (and decreases) in PTSD symptoms. Importantly, Foa and colleagues (2002) have reported that only a minority of participants showed an acute substantial increase in PTSD symptom severity during Prolonged Exposure treatment, and that this acute increase was not associated with an increased risk for dropout or poor treatment outcome. Nevertheless, to protect against risk, we will monitor participants for undue distress reactions and will use a 10-point increase from baseline assessment of PTSD symptom severity that is sustained for 3 weeks as a guide for potentially withdrawing a participant from the study treatment. If a participant is withdrawn from the study treatment, they will be followed by study personnel, if they agree to be followed, to ensure that they have received adequate clinical care. In addition, if they agree, the study will continue to conduct assessments with the participant. In addition, participants who are deemed ineligible to enroll in the trial will be referred to the appropriate VA mental health clinic. The PI or site PI will subsequently contact (within one week) these veterans to make sure that they have not experienced any barriers in following through with clinical referrals.

## 12. Adverse Event/Unanticipated Problems Reporting Plans

### **Protocol for Reporting Adverse Events**

Any study-related unanticipated problem and any type of AE or SAE, will be reported immediately to the PI, who will then report the event to the local IRB per VABHS standard operating procedures. In addition, for SAE's, the PI will submit a SAE form to the local IRB and the DMC within 48 business hours of becoming aware of SAE. Staff will keep a copy of this SAE form on file at the study site. The information to be reported will include the subject number, a description of the event, date of onset, current status, whether or not the treatment was discontinued, the reason why the event is classified as serious, and the PI assessment of the association between the event and the study treatment. [name] will provide any significant new information regarding ongoing SAEs promptly (i.e., within 48 business of becoming aware of event) to the DMC. Adverse events not designated as serious will be reported to DMC on a quarterly basis and annually to the respective local IRB.

The other two recruitment sites will follow the same procedures for reporting of adverse events and unanticipated problems, with the addition of also notifying the study PI at VA Boston.

